GENERAL INFORMATION

Evaluation of a Letter Intervention Among At-risk Adults Promoting a Plant-based Diet Using a Combination of Provider Testimonials, the Forks Over Knives Documentary, and Commitment- or Prevention-focused Behavioral Nudges

[name].

[contact]

March 25, 2022

Version 1.1

OBJECTIVES

Our mission is to promote healthier eating behavior and to reduce costs associated with healthcare. The purpose of this study is to evaluate the effects of mailing randomly selected participants a letter promoting a plant-based diet. Depending on the experimental condition, participants may additionally receive a free documentary, Forks Over Knives, and they may also get letters which use commitment- or prevention-focused messages to encourage watching the documentary and changing their eating behavior. We hypothesize that receiving the documentary will be associated with lower insurance claims and improved health outcomes one and two years later. We also hypothesize that using either commitment- or prevention-focused messages will also contribute to lower insurance claims and improved health outcomes compared to experimental conditions where materials did not include these messages.

BACKGROUND AND RATIONALE

Heart disease and diabetes are the first and seventh leading causes of death in the United States, respectively (Xu J, Murphy SL, Kochanek KD, 2016). Further, these medical conditions put a large strain on the economy. In 2016, treating cardiovascular disease in the United States costed \$555 billion, while in 2017, diabetes contributed to \$327 billion in medical costs and reduced productivity (American Diabetes Association, 2018; American Heart Association, 2017).

To address these problems in a cost-effective way, multiple randomized control trials have provided evidence that interventions that change people's lifestyles can reduce the risk of heart disease and diabetes (for reviews, see Artinian et al., 2010; Dunkley et al., 2014; Wing et al., 2001). Many of these interventions involved structured programs such as diet and exercise schedules, group sessions, and individual counseling. These programs are still costly in terms of time and personnel commitment and may be difficult to scale up to a larger population. We aim to test whether simply sending people a letter and some materials promoting a healthy diet can by itself promote behavior change and improved health outcomes.

Overall, the current study tests the effectiveness of a relatively low-cost intervention – a documentary promoting a plant-based diet – to reduce healthcare costs and improve health outcomes. This study will also test whether the use of commitment and prevention nudges can encourage more participants to watch the documentary and make lifestyle changes. The findings from this study will help researchers, hospital administrators, and health insurance companies design economical, evidence-supported programs that can improve people's health.

PROCEDURES

Research Design

We will use an experimental study with a factorial design (14 groups: 1 control, 1 letter only, 3 methods of documentary distribution x 4 behavioral nudges; see Detailed Study Procedures). We will also gather outcome data from five years before the intervention to two years after the intervention in order to allow pre-intervention and post-intervention analysis (which includes a primary analysis to be conducted one year after the intervention and a follow-up analysis the following year).

Study Population

Target Population and Inclusion/Exclusion Criteria. We will include Geisinger Health Plan (GHP) policy holders who are aged 18 and older. Participants should meet the following criteria:

- Has two out of the three following medical conditions:
 - Body mass index over 30
 - Diagnosis of type 2 diabetes (specifically, with at least one medication)
 - Diagnosis of cardiovascular disease
- Has health insurance through Geisinger Health Plan (is an active member with a full 12-month enrollment in the previous year) under one of the following categories:
 - Medicare with required primary care provider
 - Medicaid
 - Individual policy under the Affordable Care Act
- Has visited their primary care provider in the past 12 months
- Is not institutionalized
- Does not have cancer, cirrhosis, renal failure, dementia, or active psychosis
- Is not in the same household (spouse or adult child sharing the same address) as another selected participant

Participant Enrollment. There will be two steps in selecting participants for enrollment. For the first step, as many as 15,000 participants will be randomly selected. These are all participants who fulfill the inclusion criteria (based on an estimate from Geisinger Health Plan actuaries). Of this set, 8,800 will be mailed the intervention materials and the remainder (as many as 6,200, based on estimates from the GHP) will be in a control group that will not be contacted or sent any materials. For the second step, all household members (i.e., spouses or adult children sharing the same address) who are also GHP members regardless of inclusion criteria will be included in the data analysis. We need to expand the participant enrollment to these people since we expect that any materials sent to one person may be viewed and discussed by other people in the household. In effect, we are selecting 15,000 households (i.e., households that have eligible participants) and examining the claims and health data of all adult GHP members of that household. To account for these additional participants, we multiplied the number of households by 5, assuming a spouse and as many as three adult children per household, for a maximum sample size of 75,000 participants. Note that this is a generous upper limit to prevent having to stop data collection due to accidentally exceeding a smaller sample size limit. To simplify the discussion of recruitment and experimental groups, we will discuss our proposed plans at the household level, where most of the work will be conducted. For example, the random selection and assignment into experimental groups is done at the level of the household (i.e., 15,000 households selected) and only one set of materials will be sent to each household (as opposed to sending materials to each household member).

Recruitment and Screening Procedures. Geisinger Health Plan actuaries will have access to insurance and medical information necessary to identify eligible participants (see attached document, *Proposal to Receive Data from GHP*). They will then randomly select 15,000

households (see Participant Enrollment) to be enrolled in the study and randomly assign them to the 14 experimental groups. They will then give mailing information (names and addresses) to the Geisinger mailroom, who will address and mail the study materials. No recruitment or advertisement materials will be used. Our first contact with any households assigned to receive the intervention will be through the mailed study materials. If a household has multiple members, any materials will be addressed to all members of the household.

Detailed Study Procedures. Households will be randomly assigned to one of 14 experimental groups:

- Control group (1): 6,200 households will not be contacted, but their insurance and health data will be examined. This number is an estimate of the remainder of eligible participants who were not selected for other experimental groups. We plan to analyze the data of all remaining participants, as this increases statistical power for analysis without any additional cost in sending materials.
- Letter group (2): 2,200 households will receive a letter promoting a plant-based diet. This letter will feature a personal testimonial about the benefits of this diet (see attached document, Letter Versions).
- Groups 3-14 (550 households each) will receive a letter promoting a plant-based diet and the Forks Over Knives documentary. All of these households will be given a form and online link where they may choose to order a book that has more information on plant-based diets as well as a number of recipes. The groups will vary based on the method of delivering the documentary and the presence or absence of behavioral nudges in the letter. All possible combinations total to 12 groups.
 - Method of delivering the documentary
 - Online link
 - DVD
 - Online link and DVD
 - Behavioral nudge in the letter (see attached document, Letter Versions)
 - No nudge: There are no behavioral nudges included in the letter.
 - Commitment nudge: At the end of the letter promoting a plant-based diet, participants will be asked to write dates and personal signatures committing to watching the documentary. They will be asked to mail back this written commitment.
 - Prevention nudge: As part of the letter promoting a plant-based diet, one paragraph will describe the risks of not taking action. This phrasing reframes the status quo as contributing to future loss (e.g., costs of medication and operations).

We will record which households ordered the book and mail them the book. We will also record which participants mailed back written commitments.

To compare pre-intervention and post-intervention insurance and health data, we will use the following data (see data management and confidentiality section for more details on personnel with access to identifiable data):

- Geisinger Health Plan (GHP) actuaries will provide the initial participant list. This data includes identifiable data (name, date of birth, address, medical record number), but it will be processed by GHP actuaries who already have access to this information as part of their normal job responsibilities.
- Analysts from Business Intelligence Advanced Analytics (BIAA) will provide insurance claims data (amount of claims, number of specialty/primary care physician visits, number of prescriptions) and health data (body mass index, blood pressure, hemoglobin a1c, patient health questionnaire-2). This data is identifiable (name, date of birth, address, medical record number), but it will be processed by members of the BIAA and their colleagues, all of whom already have access to this information as part of their normal job responsibilities.
- The data broker ([name]) will only have access to the identifiable data (name, date of birth, address, medical record number) in order to link these files. The other investigators will only have access to coded datasets (i.e., data stripped of identifiers).

The steps for dealing with identifiable data are detailed below:

- GHP actuaries will create a spreadsheet of all eligible participants, using inclusion and exclusion criteria (see Target Population and Inclusion/Exclusion Criteria).
- The data broker ([name]) will receive this spreadsheet and will randomly assign participants to experimental groups. He will generate a spreadsheet of participant names, and addresses, information on which participants are part of the same household, and codes indicating experimental group the household is in.

Participant Withdrawal. Participants are free to engage with the mailed materials to any degree that they choose. They may even choose not to open or read the materials. Regardless of how they respond other materials, their insurance and health data will still be analyzed, as with the participants in the control group.

STUDY DATA DETAILS

Data Management Procedures and Confidentiality. Paper data will be in the form of mailed commitment and book order forms. They will be handled by the Geisinger mailroom and [name]. This includes identifiable information (names and addresses) and will be stored in locked file drawers in the Geisinger mailroom, the Autism and Developmental Medicine Institute, and Geisinger Office Building 1. After study completion, these files will be moved to a locked file drawer in Geisinger Office Building 1 and will be stored for 3 years.

All other data will be electronic and stored in password-protected spreadsheets on the investigators' password-protected computers. Datasets with identifying information will only be stored on password-protected computers of the data broker ([name]) for the purpose of linking datasets from different sources. These data will be stored in Geisinger's Virtual Desktop Infrastructure, which will have its own backup system. After all data have been linked in a de-identified, coded file, the datasets with identifiable information and any codes needed to link the identifiable information will be deleted. After the de-identified data have been fully analyzed, the de-identified dataset will be shared along with other publications from this study. The deidentified data will not be destroyed or removed after any period of time has elapsed. We intend to permanently and securely archive the deidentified dataset in order to be consistent with the best practices for open and reproducible science, as well as our obligation to the public as researchers.

Access to identifiable and protected health information will be limited to the following departments and people:

- Names and addresses only
 - Geisinger Mailroom
- Names, addresses, and electronic health records
 - GHP actuaries
- Names, medical record numbers, and electronic health records
 - BIAA analysts

- Names, addresses, medical record numbers, and electronic health records
 - [name] (data broker)

Risks. This study poses no more than minimal risk for participants. The letter participants will receive only mentions a vegetarian diet, with no specific plan recommended for participants (see attached document, Letter Versions). Although the topic of health may cause some stress for people, the letter would be similar to an everyday conversation about health and nutrition. In addition, Forks Over Knives is a PG-rated documentary that is already available on common media outlets like Netflix. Still any potential risks are noted below.

- Participants may attempt to make medicinal changes without professional guidance. We try to reduce this possibility by clearly stating in the letter that the materials are not professional medical advice and that they should consult with a doctor before making any changes to their medication.

- There is little risk for loss of confidentiality. Only a few people have access to identifiable data and most of them only have access to names and addresses. Only GHP actuaries, BIAA analysts (both as part of their occupation) and [name] will have access to protected health information, and both are within the Geisinger Health System.
- There are no known political, economic, or social burdens that participants might face as part of this research.
- There may be some suspicion of goals of the investigators and of the Geisinger Health Plan if people figure out that only certain people are targeted. For this reason, only individual (and not group) plans were included to prevent discussions among people who share the same plan.

Benefits. Participants who receive any level of the intervention will potentially learn beneficial information about the importance of lifestyle to health and specifically, about plant-based diets. However, as we do not prescribe or enforce a specific action, there is a wide range of possible benefits. Regardless, participants are given educational materials in the form of a documentary and a book with more information and recipes (if they choose to request the book). Even without specifically following the recommendations of the documentary or book, participants may become motivated to take better care of their health by setting goals, consulting with medical professionals, or making other lifestyle changes. Any of these behaviors can result in increased knowledge about personal health, improved health outcomes, and reduced spending on healthcare.

BIBLIOGRAPHY

## Statistical Analysis Plan

### Project Status

All interventions have been launched and data collection is ongoing. The time period for the primary outcomes (1 year pre-intervention, 1 year post-intervention) has already elapsed, and the analysis will focus on this time period. The data have not been examined as of the time this document has been posted.

Due to delays in pulling claims-level data from the Geisinger Health Plan, we currently do not have access to 3 of the 6 primary outcomes: (1) change in number of visits, (2) change in number of prescriptions, and (3) change in number of unique prescribed medications. The plans outlined below will still be followed for these outcomes if we are later able to acquire these data. The key primary outcome – change in medical cost – was collected, as were the other primary and secondary outcomes.

### Planned Analyses

We currently have 7 primary and 6 secondary outcome variables, with timeframes for analysis relative to the intervention date outlined below.

Outcome	Desired Level	Primary Analysis	Secondary Analysis 1	Secondary Analysis 2
Medical Cost	Lower	1 year pre, 1 year post		5 years pre, 2 years post
Visits*	Lower			
Number of Prescriptions*	Lower			
Number of Unique Prescribed Medication*	Lower			
Body Mass Index	Between 18.5 to 25			
Systolic Blood Pressure	< 120 mmHG			
Diastolic Blood Pressure	< 80 mmHG			
Triglyceride Level	< 150 mg/dl	1 year pre, 1 year post		
Low-density Lipoprotein (LDL) Level	< 100mg/dl			
High-density Lipoprotein (HLD) Level	< 60 mg/dl			
LDL/HDL Ratio	< 3 for men, < 2 for women			
Hemoglobin A1c (hba1c)	< 5.7%			
Depressed Mood and Anhedonia (PHQ-2)	Lower			

\* Data currently unavailable

For clarity in this plan, the different conditions (and planned sample sizes) of the study are presented below. Passive control participants who are missing all outcome data and all other participants who returned mail (e.g., wrong address; did not accept mail) will be excluded from the analysis.

Passive Control	Active Control (Letter with no Video)	Letter with Video			
		Link	DVD	DVD + Link	
2200	2200	550	550	550	Letter Only
		550	550	550	Commitment Nudge
		550	550	550	Prevention Nudge
		550	550	550	Commitment + Prevention
2200	2200	2200	2200	2200	

The overall hypothesis for this project is that the experimental conditions (e.g., participants who received Forks Over Knives materials; shaded yellow in the figure above) should have better outcomes compared with those in the control conditions, one year after the intervention. All outcomes are hypothesized to shift in the direction of the desired levels (i.e., lower costs, better health). Among the primary outcomes, cost is of greatest interest and importance, as it encompasses multiple other outcomes.

### Primary Analysis and Secondary Analysis 1

As we are interested in the change in each outcome between 1 year pre-intervention and 1 year post-intervention, mixed-effects regression models will be used for continuous outcomes, using a log-link function and negative binomial distribution for outcomes involving highly positively skewed count or count-related data: costs, visits, number of prescriptions, and number of unique medications. A mixed-effects logistic regression will be used for binary outcomes.

Question 1: Does getting Forks Over Knives materials lead to improved outcomes over controls?

Passive Control	Active Control (Letter with no Video)	Letter with Video			
		Link	DVD	DVD + Link	
2200	2200	550	550	550	Letter Only
		550	550	550	Commitment Nudge
		550	550	550	Prevention Nudge
		550	550	550	Commitment + Prevention
2200	2200	2200	2200	2200	

Data for all participants who received Forks Over Knives materials (in yellow above) will be collapsed into one group.

Main analysis 1: Active Control, Passive Control vs. Forks Over Knives (reference group)

Exploratory analysis 1: Active Control vs. Passive Control (reference group)

Question 2: Do the behavioral science-informed components in the letter lead to improved outcomes over the controls?

Passive Control	Active Control (Letter with no Video)	Letter with Video			
		Link	DVD	DVD + Link	
2200	2200	550	550	550	Letter Only
		550	550	550	Commitment Nudge
		550	550	550	Prevention Nudge
		550	550	550	Commitment + Prevention
2200	2200	2200	2200	2200	

Data for all participants within each behavioral nudge condition (in yellow, green, grey, and white above) will be collapsed into one group.

Main analysis 2: Commitment Nudge, Prevention Nudge, Commitment + Prevention vs. Letter Only (reference group)

Main analysis 3: Commitment Nudge, Prevention Nudge, Commitment + Prevention, Letter Only vs. Active Control (reference group)

Main analysis 4: Commitment Nudge, Prevention Nudge, Commitment + Prevention, Letter Only vs. Passive Control (reference group)

Exploratory analysis 2: Commitment Nudge, Prevention Nudge vs. Commitment + Prevention (reference group)

Exploratory analysis 3: Commitment Nudge vs. Prevention Nudge (reference group)

Question 3: Does medium (DVD, Link, DVD + Link) influence outcomes?

Passive Control	Active Control (Letter with no Video)	Letter with Video			
		Link	DVD	DVD + Link	
2200	2200	550	550	550	Letter Only
		550	550	550	Commitment Nudge
		550	550	550	Prevention Nudge

		550	550	550	Commitment + Prevention
2200	2200	2200	2200	2200	

Data for all participants within each medium condition (in yellow, green, and grey above) will be collapsed into one group.

Exploratory analysis 4: DVD, Link, DVD + Link vs. Active Control (reference group)

Exploratory analysis 5: DVD, Link, DVD + Link vs. Passive Control (reference group)

Exploratory analysis 6: DVD, Link vs. DVD + Link (reference group)

Exploratory analysis 7: DVD vs. Link (reference group)

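### The SAP sets the desired HDL level as a ceiling of 60 mg/dl, which at fixed LDL reads a change in HDL around or above 60 the opposite way from the LDL/HDL ratio row

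*SAP*

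**What the plan says.** The outcome table in the SAP, Planned Analyses, gives a desired level for each of 13 outcomes. Three rows matter here:

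- HDL: "High-density Lipoprotein (HLD) Level < 60 mg/dl"
- LDL: "Low-density Lipoprotein (LDL) Level < 100mg/dl"
- LDL/HDL ratio: "< 3 for men, < 2 for women"

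The text after the table turns that column into the hypothesis: "All outcomes are hypothesized to shift in the direction of the desired levels (i.e., lower costs, better health". Questions 1 and 2 are then framed as improvement: "Does getting Forks Over Knives materials lead to improved outcomes over controls" and "Do the behavioral science-informed components in the letter lead to improved outcomes over the controls". Continuous outcomes are to be analysed as change from one year before to one year after the intervention. The SAP adds: "A mixed-effects logistic regression will be used for binary outcomes". It does not identify any of the 13 outcomes as binary.

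Nothing else in the text available for review gives a direction for HDL (one portion of the SAP was not included). The Protocol's list of health data, under Detailed Study Procedures, contains no lipids.

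**The concern.** The desired-level column is the only place where the SAP says what counts as a good result for HDL. Written as a ceiling, it makes a drop from above 60 to below 60 a success and a rise above 60 a failure. The ratio row also sets a ceiling, but with HDL in the denominator, so at a given LDL a higher HDL moves the ratio in the favourable direction.

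One change in HDL could therefore be reported as improvement in one row and deterioration in the next. At stake is whether an HDL result is presented as supporting or contradicting the hypothesis. If outcomes were coded as at or off target, the coding of individual participants would also be affected.

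**Working it through.** **Inputs.** From the SAP table: HDL below 60; LDL below 100; ratio below 3 (men) or below 2 (women). The individual LDL and HDL values used below are assumed for illustration, because the documents give no lipid distribution. The plan states no figure to reproduce; the check is of direction and of the cut-offs.

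**Direction.** Ratio = LDL / HDL. At fixed LDL the ratio falls whenever HDL rises, and rises whenever HDL falls.

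**Inside the SAP's own LDL target.** For anyone with LDL below 100 and HDL of 60 or more, the ratio is below 100/60 = 1.67. That person meets the LDL limit and both ratio limits but is off target on HDL.

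**A change at LDL 95, HDL 65 to 55.**

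- HDL row: moves from off target to on target.
- Ratio: 95/65 = 1.46 to 95/55 = 1.73, a rise of 65/55 − 1 = 18.2%. Neither ratio cut-off is crossed, so the conflict here is one of direction.
- Break-even: HDL has fallen by 1 − 55/65 = 15.4%. The ratio improves only if LDL falls by more than that, to below 95 × 55/65 = 80.4.

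**Can the cut-offs be met together?** Meeting the HDL and ratio rows together requires LDL/k < HDL < 60, with k = 2 (women) or 3 (men). This is possible when LDL is below 2 × 60 = 120 (women) or 3 × 60 = 180 (men). At LDL 95 all three lipid rows are met for HDL between 95/2 = 47.5 and 60 (women), or between 95/3 = 31.7 and 60 (men).

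**When do the cut-offs themselves flip in opposite directions?** Take HDL rising from 55 to 65, which leaves the HDL target:

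| Case | Ratio at HDL 55 | Ratio at HDL 65 | Ratio row |
|---|---|---|---|
| Woman, LDL 120 | 120/55 = 2.18 | 120/65 = 1.85 | enters target (< 2) |
| Man, LDL 180 | 180/55 = 3.27 | 180/65 = 2.77 | enters target (< 3) |

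Both examples have LDL outside the SAP's LDL target.

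**When is there no conflict?** If HDL stays below 60 throughout, the HDL row is met before and after and sets no further direction. HDL and the ratio can also fall together if LDL falls proportionally more: 100/50 = 2.00 to 90/48 = 1.88.

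**Analyses concerned.** Main analyses 1 to 4 and exploratory analyses 1 to 3 sit under Questions 1 and 2, so 4 + 3 = 7 listed comparisons carry the improvement wording for HDL.

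**The case against.** The strongest reply is that this has little practical effect. The planned models compare change in a continuous outcome between groups, whereas the examples are individuals crossing 60. If group HDL lies below 60, the literal row gives no direction, which is milder than a wrong one. LDL is itself hypothesised to fall, so holding it fixed is not the SAP's own scenario, and the three lipid cut-offs can be met together. No one-sided test depends on the entry, so all seven estimates are the same either way. The misspelt abbreviation in the row suggests a slip, and the hypothesis is glossed as better health, so a reader may well infer what was meant. Finally, the ratio row limits HDL only relative to LDL, so it does not by itself establish that HDL should rise, still less that 60 is a floor.

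Most of this stands as a limit on size. An opposite reading of a group result depends on where HDL lies, how LDL moves and whether at-target coding is used. The documents settle none of these. It is also right that the documents do not establish 60 as a floor.

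It does not remove the inconsistency. That the cut-offs can be met jointly does not settle the direction of a change, which is what the SAP hypothesises. The general reference to better health does not override a specific entry. If the entry is a slip, that is a reason to correct it openly, because a silent reinterpretation after the results are known cannot be told apart from a post hoc choice. The ratio row is the only internal evidence on HDL direction, and at fixed LDL it favours higher HDL.

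**Conclusion.** The concern holds. As written, the HDL entry gives a direction that, for HDL around or above 60 and LDL held fixed, is opposite to that of the ratio row. This is so even within the SAP's LDL target.

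The effect is confined to the hypothesised direction and interpretation of one of six secondary outcomes, and to at-target coding if any is planned. The HDL model estimate, the primary cost analysis and the sample size are untouched. How many participants are affected cannot be computed from the documents.

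The conclusion assumes that the inequality sign in the text reviewed matches the source file. The neighbouring rows have the same form, which makes an extraction error unlikely, but the source should be checked. The point should be corrected; it does not threaten the trial's main conclusion.

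**What to change.** 1. Reconcile the HDL row with the ratio row by correcting the HDL entry so that higher HDL is the desired direction, and add a sentence stating that the HDL hypothesis is an increase.
2. Have the sponsor confirm the intended cut-off from its source rather than simply reversing the sign at 60.
3. State whether any outcome will be analysed as at or off target. If HDL is, make the coding follow the corrected direction.
4. Make the change before the data are examined. Under Project Status the SAP says: "The data have not been examined as of the time this document has been posted". If that is no longer true, date the change and disclose it.

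The cost is one table entry and one sentence, with a short statement on binary coding and, if needed, a dated note. Sample size, models and group comparisons stay as they are.

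### The SAP excludes people for missing all outcome data in the passive-control arm only, which can bias the passive-control contrasts in a direction the documents do not settle

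*SAP*

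**What the plan says.** In the SAP, under Planned Analyses, the sentence above the table of conditions sets two exclusions that differ by arm. In passive control it removes "Passive control participants who are missing all outcome data". In the active-control and video arms the ground is different: "all other participants who returned mail (e.g., wrong address; did not accept mail) will be excluded from the analysis". No missing-data exclusion is stated for any arm that was sent a letter.

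The SAP treats outcomes as changes. Under Project Status: "The key primary outcome – change in medical cost – was collected". Under Planned Analyses: "As we are interested in the change in each outcome between 1 year pre-intervention and 1 year post-intervention, mixed-effects regression models will be used". It does not say whether the clause refers to the pre-year, the post-year or both. Nor does it say whether a member with no claims has cost recorded as zero or as missing.

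The protocol contains no such exclusion. Of the control group it says "We plan to analyze the data of all remaining participants". Of people who ignore the mailing it says "their insurance and health data will still be analyzed, as with the participants in the control group". Index participants had to meet two entry conditions that bear on this: "Has visited their primary care provider in the past 12 months" and "is an active member with a full 12-month enrollment in the previous year". Other household members are included without meeting the entry criteria and are analysed separately.

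**The concern.** Whether a person has outcome data after the mailing date is known only after randomisation and depends partly on use of care and on staying in the plan. Randomisation puts the same share of such people in every arm. Removing them from one arm alone means that passive control no longer represents the same population as the arms compared with it.

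Medical cost, which the SAP calls its key primary outcome, is the most exposed. For a blood-pressure or HbA1c reading, no record means no value. For cost, no record may mean zero, and the plan does not say which coding applies.

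At stake are the contrasts that use passive control: the passive part of Main analysis 1, Main analysis 4, and Exploratory analyses 1 and 5. Main analyses 2 and 3 and the active-control part of Main analysis 1 compare mailed arms with each other, so this clause does not touch them.

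**Working it through.** The plan gives no figure for this clause, so there is none to reproduce. The check is what each reading does when the mailing has no effect.

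Notation, all values assumed:
- Mean cost is 1 in each arm in each year, before any exclusion or missing value.
- f is the share of people the clause describes, equal across arms by randomisation.
- a is their pre-year cost relative to the mean.
- R is the mailed arm's post/pre ratio divided by that of control. R below 1 looks like a saving.

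**Reading 1: every outcome missing in both years, same coding in all arms.** Mailed counterparts have no data either and add nothing to a likelihood-based mixed model, so R = 1.00. For index participants f is also close to zero, because entry required a primary-care visit and full enrolment in the previous year.

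**Reading 2: judged on the post-year, mailed counterparts kept at zero cost.**
- Control after exclusion: post mean 1/(1−f), pre mean (1−fa)/(1−f), change 1/(1−fa).
- Mailed change: 1.
- R = 1 − fa.

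| f | a = 0 | a = 0.5 | a = 1 |
|---|---|---|---|
| 1% | 1.000 | 0.995 | 0.990 |
| 2% | 1.000 | 0.990 | 0.980 |
| 5% | 1.000 | 0.975 | 0.950 |

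At half-average pre-year cost the false saving is half the share dropped. People with zero cost in both years (a = 0) cause no shift on the change scale.

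**Reading 3: judged on the post-year, post-year cost missing in all arms.** A control without post-year data has no change and is dropped. The mailed counterpart keeps a pre-year record in the mixed model. Let m be the observed post mean, the same in both arms.
- Mailed change: m/1. Control change: m(1−f)/(1−fa).
- R = (1−fa)/(1−f).
- f = 3%, a = 0.5: 0.985/0.97 = 1.015 (log 0.015).
- f = 5%, a = 0.5: 0.975/0.95 = 1.026 (log 0.026).
- f = 5%, a = 1.5: 0.925/0.95 = 0.974.

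For people with low pre-year cost the shift runs opposite to Reading 2; for people with high pre-year cost it turns round again. This compares observed means. A mixed model weights pre-only records differently, so only the sign and rough size carry over.

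**The other half of the sentence.** Suppose a share r of mailed participants is removed for returned mail, with cost c relative to the mean. The post-year ratio, mailed over control, with zeros kept in the mailed arms, is (1−f)(1−rc)/(1−r).
- f = 2%, r = 5%, c = 0.5: 0.98 × 0.975/0.95 = 1.006.
- f = 2%, r = 10%, c = 0.5: 0.98 × 0.95/0.90 = 1.034.
- f = 5%, r = 5%, c = 0.5: 0.95 × 0.975/0.95 = 0.975.
- f = 2%, r = 5%, c = 1.5: 0.98 × 0.925/0.95 = 0.954.

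Returned mail can therefore cancel, reverse or enlarge the shift.

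**Simulation check.** Overdispersed counts were simulated with no true effect, 6,600 (12 × 550) video against 2,200 control, 200 replicates. Reading 2 with average pre-year cost gave change ratios of 0.977, 0.949 and 0.898 at f = 2%, 5% and 10%; the formula gives 0.98, 0.95 and 0.90. Removing the same people from both arms gave 1.003, 0.996 and 1.001.

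**The case against.** The strongest reply is that bias needs different coding by arm, which no text supports. The protocol describes one outcome extraction, by the same analysts, for all groups. If no claims is recorded as zero, such a control has cost data and is not missing everything. If it is recorded as missing, the mailed counterpart has no cost either. This stands for Reading 1. It does not dispose of Reading 3: coding there is uniform, yet the mailed person's pre-year data stay in the model while the control's are removed.

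It is also fair that missing everything is far narrower than not using care. Cost and every available clinical measure must be absent, in people who had two of three chronic conditions and a recent primary-care visit. The affected share may be very small.

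The two protocol sentences on whose data are analysed do not contradict the SAP outright. One explains why the control group takes all remaining eligible people; the other concerns recipients who do not engage. Neither addresses people with no data. What stands is that the SAP adds an exclusion the protocol does not contain and gives no reason for limiting it to one arm.

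A reader might infer that the clause creates a spurious saving in favour of the documentary. That follows only under Reading 2, with dropped controls who had pre-year costs and no offset from returned mail. The documents establish none of these conditions.

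**Conclusion.** The point holds as a possible bias of undetermined direction and size. The SAP states a one-arm, post-randomisation exclusion. On any reading that looks at post-year or change data, it can distort the passive-control contrasts. At assumed shares of 1% to 5% and half-average pre-year cost, R runs from 0.995 to 0.975 if mailed counterparts count as zero. If their post-year cost is missing, R is above 1, about 0.02 to 0.03 log units at 3% to 5%. If all outcomes in both years must be missing and coding is uniform, R is 1.00 and the clause is not needed.

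Every value of f, a, r and c is an assumption; the documents give none. False-positive rates should not be attached to this point, since they would also need an assumed cost variance and a model structure that the SAP leaves open. The case for change is that none of the readings examined needs a rule confined to one arm, and some are harmed by it.

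**What to change.** Delete the passive-control clause and state one rule for all arms, for example:

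*No participant is excluded for lacking outcome data in one arm only. An enrolled member with no claims in a window has cost, visits and prescriptions of zero for that window, in every arm. Members who disenrolled or are not found in the data extraction are treated as missing, identically in every arm. Exclusions are counted and reported by arm.*

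Visits and prescriptions are not yet available to the study team; the rule would apply if they are obtained. Clinical measures with no reading remain missing in every arm.

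The returned-mail exclusion in the same sentence needs its own decision, because returned mail cannot be observed in a group that was sent nothing.

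The cost is one SAP sentence, an enrolment flag for each window and a count by arm. The SAP states that the data had not been examined when it was posted; the change should be made and dated before they are.
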